### **3.0 Methods & Procedures**

#### **3.1 Study procedures and assessments.**

- **Screening and Enrollment:** Prospective subjects will be considered for entry into the study. Subjects meeting the inclusion and exclusion criteria will be informed of the opportunity to participate in the study. Subjects will be entered into the study after providing written informed consent. Each subject will be instructed that if they decide not to participate, they may withdraw at any time.
- **Randomization:** Netarsudil ophthalmic solution 0.02% and placebo eye drops will be dispensed to study subjects in 2.5 ml bottles, identical in appearance. A designated, unmasked, dosing coordinator will apply a coded sticker to each bottle. A computer generated randomization table will be generated. During the routine follow up exam 1 or 2 days after transplantation, the study subject will be randomly assigned to receive netarsudil or AR-13324 placebo (netarsudil vehicle). Both the subject and the investigator will remain masked as to the assigned treatment. If a study participant elects to have both eyes enrolled in the study, the dosing coordinator will automatically assign the second eye to the opposite treatment group from that of the first eye.
- **Study Treatment Regimen:** Subjects will be instructed to instill the assigned eye drop into the study eye once nightly for the 9-month study duration. As standard of care to prevent cornea transplant rejection, subjects will use prednisolone acetate 1% eye drops 4 times daily for the first 3 months, then 3 times daily during month 4, twice daily during month 5, and once daily during months 6 to 9.
- **Study Drug Accountability:** Subjects will be asked to bring back to the clinic all study bottles, both used and un-used. All study drug bottles will be reconciled and recorded.
- **Rescue Medication:** if a study subject develops IOP elevation (a measurement  $\geq 24$  mm Hg or an increase over the screening pre-operative reading of  $\geq 10$  mm Hg), the dosing coordinator will be notified. If the affected eye was assigned to the placebo group, the subject will be offered the opportunity to crossover to the netarsudil group to determine whether that adequately reduces IOP. Depending upon the severity of the IOP increase, the investigator may decide whether it is in the patient's best interest to reduce corticosteroid strength and/or dosing frequency and/or initiate use of approved glaucoma medications.
- **Examinations:**

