- Schedule: Each subject will be examined at screening, 1, 3, 6 and 9 months after endothelial keratoplasty as detailed in Table 1. The examination schedule and procedures are standard of care for endothelial keratoplasty patients.
- Procedures: At 5 day, 1, 3, 6, and 9 month exams, medical and ophthalmic histories will be updated, adverse events will be recorded, and measurements of visual acuity will be made. At 1, 3, 6 and 9 month exams, measurements of manifest refraction, corneal thickness (pachymetry) and intraocular pressure will be made. Corneal endothelial cell density will be measured by specular or confocal microscopy if possible.. A slit lamp examination will be performed to assess the health of the transplant and document any conjunctival or lid hyperemia, stromal inflammation, superficial punctate keratitis, other surface toxicity of the cornea, neovascularization of the cornea, cells or flare in the anterior chamber, or evidence of transplant rejection.
- Records release: Subjects may be asked to sign a records release form in case the subject sees another eye specialist while enrolled in the study. This will allow the investigator to determine if there is a rejection episode or elevated intraocular pressure at examinations made with other physicians. The primary outcome (intraocular pressure) is a routine ophthalmic exam procedure, so the subject may have some exams performed by a local eye doctor if returning to the study site for all exams is too burdensome.
- Unscheduled examinations: Subjects will be instructed to return for extra examinations if they note any problems with the eye or any early signs of a possible rejection episode, such as a change in vision, redness to the eye, increased light sensitivity, burning sensation, or foreign body sensation.
- Study completion: Subjects will be considered to have completed the study after they complete the 9-month examination.
- Subject withdrawal or discontinuation: Each subject may voluntarily discontinue the study at any time they choose. Subjects who cannot complete the study for administrative reasons (e.g., non-compliance, failure to meet visit schedule, etc.) will be discontinued from the study. Discontinued subjects may be replaced. For

subjects withdrawn from the study, the same measurements and assessments should be performed as done at the 9-month exit exam. Adverse events should be followed up until resolution or stabilization of the adverse event.

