#### **4.0 Risk/Benefit Assessment**

##### **4.1 Risks and Anticipated Adverse Events:**

Risks: This study is considered moderate risk. Netarsudil is an investigational drug - a New Drug Application (NDA) was recently submitted to the U. S. Food and Drug Administration.

A number of complaints and complications are anticipated in patients who have received a cornea transplant, regardless of whether they participate in this study. Therefore, the presence or absence of the following anticipated complaints and complications in the study eye will be recorded on the electronic case report form (eCRF) for each exam rather than on separate adverse event forms.

- Complaints of ocular discomfort: (examples include: eye pain, irritation, burning, itching, scratchy feeling, foreign body sensation, tired/fatigued feeling, achy/tender/sore feeling, pressure sensation, tightness, twinge/twitchy feeling, dry eyes, tearing/watering, eye redness)
- Complaints of visual symptoms or disturbances: (examples include: glare or fluctuating vision, haloes around lights, diplopia, blurry, hazy, cloudy, filmy or out of focus vision, ghosting or shadowing, difficulty reading, difficulty with night driving, floaters, spots in vision, light sensitivity, decreased vision, light reflections from intraocular lens or peripheral iridotomy).
- Increased ptosis (within the first 6 months of surgery)
- Puffy eyelids (within the first 3 months of surgery)
- Delayed resolution of corneal haze or edema (within the first 6 months of surgery)
- Subconjunctival hemorrhage (within the first 3 months of surgery)
- Epithelial defect (within the first month of surgery)
- Folds in the transplant

- Partial graft detachment without further intervention
- Development of capsular haze
- Superficial punctate keratitis
- Pupillary block (within the first 3 months of surgery)

Adverse events: The type, severity, duration and frequency of the following anticipated adverse experiences and any other unanticipated ocular adverse events will be tabulated. If a patient experiences an adverse reaction, appropriate medical treatment will be provided. Examples may include:

- Graft detachment which requires intervention
- Immunologic graft rejection episode
- Graft failure and/or regraft
- Intraocular pressure elevation which requires intervention
- Development of capsular haze which requires intervention
- Iris synechia
- Cystoid macular edema
- Iritis

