Anticipated rare adverse events include retinal detachment, iris synechiae/atrophy, epiretinal membrane, infectious keratitis or conjunctivitis, branch retinal vein occlusion, or endophthalmitis.

Serious Adverse Event: A serious adverse event is one that results in any of the following outcomes: death, a life-threatening adverse event, inpatient hospitalization or prolongation of existing hospitalization, a persistent or significant disability/ incapacity, or a congenital anomaly/birth defect. In the event of a serious adverse event, the investigator will maintain complete documentation and promptly inform the governing Institutional Review Board (IRB) of the serious adverse event within their required reporting period.

Fellow eye: Patients in this population tend to be affected with the eye condition bilaterally, so many of the study subjects may undergo surgery on the fellow eye during study participation.

Routine fellow-eye post-surgical complications will not be transcribed to the eCRF unless the fellow eye is enrolled in the study at the time of the event.

**4.2 Protection Against Risks:** Every effort will be made to minimize any risks or discomforts to study subjects. The investigator will ensure appropriate training of study personnel and monitoring of subjects and will provide appropriate treatment for eye-related adverse events or referral for treatment of non-eye-related adverse events. The subject and or their health insurance plan will be responsible for payment for treatment, counseling or follow up.

A **Data Safety Monitoring Committee (DSMC)** will be chaired by [name], an independent ophthalmologist practicing in Menasha, Wisconsin. The DSMC will review any serious adverse events as they occur. The DSMC will also review the interim data (including adverse events and subject compliance) every 6 months, to determine if any modifications to the original study plan may be warranted. The DSMC meeting minutes and recommendations will be documented and shared with IRBCo, Inc. and with the provider of the investigational product, Aerie Pharmaceuticals.

**4.3 Potential Benefits to the Subjects:** Study subjects may not realize any direct benefit from participation in the research; rather, important knowledge which may benefit future subjects is being sought.

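### Section 4.1 limits adverse event tabulation to ocular events, so non-ocular events, serious or not, reach no planned table comparing netarsudil with vehicle

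*Combined protocol and SAP*

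**What the plan says.** The tabulation rule is in section 4.1, under adverse events. It provides that the listed anticipated events and "any other unanticipated ocular adverse events will be tabulated", with their type, severity, duration and frequency. The examples that follow are all events of the eye or the graft, and so are the rare events listed after them. Routine post-transplant complaints are handled separately: the "anticipated complaints and complications in the study eye will be recorded on the electronic case report form (eCRF) for each exam".

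The recording provisions carry no ocular limit. Section 3.1 states, for each exam from day 5 through month 9, that "medical and ophthalmic histories will be updated, adverse events will be recorded, and measurements of visual acuity will be made". Table 1 marks adverse events at every visit from randomization on.

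Section 4.2 expects events outside the eye, but provides only for "referral for treatment of non-eye-related adverse events". It also has the Data Safety Monitoring Committee (DSMC) review serious events as they occur and adverse events every 6 months, again without an ocular limit. The serious event definition in section 4.1 covers any body system and requires documentation and a report to the IRB.

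Section 4.1 also states that "Netarsudil is an investigational drug - a New Drug Application (NDA) was recently submitted", and section 3.1 has subjects "instill the assigned eye drop into the study eye once nightly for the 9-month study duration".

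**The concern.** The summary rule is narrower than the recording rule. The word *ocular* in section 4.1 is a stated restriction, not just a missing detail, and no other section widens it. The data analysis section (3.2) deals only with IOP elevation.

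At stake is the by-treatment view of non-ocular tolerability over 9 months of nightly dosing with a drug the protocol calls investigational. The vehicle arm is what would separate background illness from a possible drug effect, and the plan leaves it unused for these events.

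There is also an attribution problem. Under section 3.1 a second enrolled eye goes to the opposite arm, and a placebo eye with IOP elevation may be offered netarsudil. A non-ocular event belongs to a person who may be using one product or both, so a table by eye cannot place it. If no rule is written beforehand, the choice would be made after the events are known.

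**Working it through.** The plan gives no figure for adverse events, so there is none to reproduce. The point rests on comparing the provisions.

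**Step 1: follow a non-ocular event through the plan.**

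| Stage | Section | Is a non-ocular event covered? |
|---|---|---|
| Recorded at visits | 3.1, Table 1 | Not excluded, but not named |
| Routine complaints on the eCRF | 4.1 | No, study eye only |
| Treatment | 4.2 | Yes, by referral |
| Serious event reporting | 4.1, 4.2 | Yes, to the IRB and DSMC; no table stated |
| DSMC review every 6 months | 4.2 | Not excluded; no by-arm format stated |
| Tabulation | 4.1 | No, ocular only |
| Statistical analysis | 3.2 | No, IOP outcome only |

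No row leads from a non-ocular event to a table by treatment. Seriousness does not change this, because the provisions for serious events concern documentation, notification and committee review.

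**Step 2: would such events occur?** Inputs from section 3.2 are 84 eyes per arm for analysis and 186 eyes recruited. Assuming equal arms, 186/2 = 93 eyes per arm. Because a second eye always goes to the opposite arm, nobody is assigned netarsudil in both eyes, so netarsudil-assigned eyes and participants are equal in number (before any crossover).

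The chance of at least one event at true frequency p among n participants is 1 − (1 − p)^n:

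- p = 1%: 57% for n = 84 and 61% for n = 93.
- p = 3%: 92% for n = 84 and 94% for n = 93.

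The frequency at which that chance reaches 95% is 1 − 0.05^(1/n):

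- n = 93: 1 − 0.05^(1/93) = 3.2%.
- n = 84: 1 − 0.05^(1/84) = 3.5%.

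**Step 3: what this does not show.** At 3.2% the expected count is 93 × 0.032 ≈ 3 events. That supports a descriptive table and little by way of comparison between arms.

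**The case against.** The strongest reply is that nothing the trial sets out to show is harmed. Section 1.1 states one objective and section 1.3 one main outcome, both concerning IOP elevation. Section 4.1 says what will be tabulated but does not forbid other summaries. Adverse events are recorded at visits, the DSMC sees them, and its minutes and recommendations go to the IRB and the product's provider. Section 4.4 allows termination for unexpected risk. If the data are in hand, a table could be added later.

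Most of this stands, and it limits the point. A reader might infer that the trial's safety conclusion is invalid, or that nothing could be said about systemic effects. The documents do not support either reading: they promise no safety conclusion, and committee review continues throughout. That review lessens the gap without closing it, because no by-arm table of non-ocular events is specified for the DSMC or for the final report.

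The assurance that a table could be added later is weaker than it looks. The text never says explicitly that non-ocular events are captured on the case report form; the only explicit statements of scope concern the eye. If capture is also ocular only, later tabulation would be impossible.

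**Conclusion.** The point holds as a gap in planned safety reporting. It is worth correcting because it is cheap to correct. It does not touch the IOP result, the sample size or the conduct of visits.

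Two further inferences should be resisted:

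- **That only non-serious events are left out.** Serious non-ocular events are reported and reviewed, but no table is planned for them either.
- **That the 3.2% figure (3.5% with 84 participants) measures power.** It shows only that events at about that frequency would very likely occur at least once.

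The figures assume equal arms, 84 to 93 participants assigned netarsudil, and independent participants with a common event frequency. The documents name no expected systemic effect of the drug, so the case rests on completeness and not on a known signal. The conclusion also takes the section 4.1 table to be split by treatment, which the section does not state.

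**What to change.** 1. In section 4.1, change the phrase to *any other unanticipated adverse events, ocular and non-ocular*, and state that the tables are by treatment.
2. Confirm in the protocol that non-ocular events, with onset dates, are captured on the case report form.
3. Tabulate ocular events by eye.
4. Tabulate non-ocular events, serious and non-serious, by participant according to the product or products in use on the onset date: netarsudil only, vehicle only, or both. Give each category its own denominator (participants exposed and exposure time), since one person can contribute to more than one.

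Dating exposure matters. Section 4.1 expects many subjects to have fellow-eye surgery during participation, so a person may move from one product to both, and crossover can change exposure again. A fixed label per participant would misplace events that precede second-eye enrolment.

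The cost is slightly more data entry, a dated exposure variable and one descriptive table. No visit, treatment or sample size changes. Precision for comparing rare events will stay low, and the table should be labelled descriptive.

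### The serious adverse event definition has no sight-threatening criterion, so an acute ocular event that the protocol anticipates could wait up to 6 months for DSMC review if treated without admission

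*Combined protocol and SAP*

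**What the plan says.** Section 4.1 defines a serious adverse event as one that leads to any outcome on a fixed list. The list opens with "death, a life-threatening adverse event, inpatient hospitalization or prolongation of existing hospitalization" and closes with "a persistent or significant disability/ incapacity, or a congenital anomaly/birth defect". It has no item for a threat to sight, for intervention to prevent vision loss, or for other medically important events.

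The sentence just before the definition reads: "Anticipated rare adverse events include retinal detachment, iris synechiae/atrophy, epiretinal membrane, infectious keratitis or conjunctivitis, branch retinal vein occlusion, or endophthalmitis". Earlier in 4.1, a separate list of anticipated adverse events includes graft detachment needing intervention, rejection, graft failure and pressure elevation needing intervention. These and "any other unanticipated ocular adverse events will be tabulated".

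Two fast routes are tied to the definition. Under 4.1, when a serious adverse event occurs, the investigator is to "promptly inform the governing Institutional Review Board (IRB) of the serious adverse event within their required reporting period". Under 4.2, "The DSMC will review any serious adverse events as they occur". For everything else, 4.2 provides periodic review: "The DSMC will also review the interim data (including adverse events and subject compliance) every 6 months".

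**The concern.** The study treatment is an eye drop used "once nightly for the 9-month study duration", and Section 4.1 calls the drug investigational. Every event on the protocol's own rare list is ocular, and 4.2 appoints an ophthalmologist to chair the DSMC, so independent review of ocular safety is evidently intended. Yet the trigger for immediate review names no ocular event.

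What is at stake is when a possible safety signal reaches the DSMC and the IRB. The investigator is masked (Section 3.1) and cannot see whether two or three such events lie in one arm. Section 3.1 also lets a local eye doctor perform some examinations. In that setting a written trigger is more dependable than case-by-case judgment about whether an event is serious.

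**Working it through.** **Inputs.** The serious adverse event list and the rare-event list come from 4.1, the two DSMC routes from 4.2, and the 9-month treatment course from 3.1. The 6-month interval is stated outright, so there is no plan calculation to reproduce.

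**Step 1: test one case against the list.** Take endophthalmitis or retinal detachment in the study eye, treated without admission, with the visual outcome good or still unknown.

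- Death or life-threatening event: not met.
- New or prolonged hospitalization: not met, because there is no admission.
- Congenital anomaly or birth defect: not applicable.
- Persistent disability or incapacity: cannot be judged at onset.
- Significant disability or incapacity: carries no duration condition, so marked vision loss at presentation could qualify that day. With good vision, or with the outcome not yet known, it need not.

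The gap is therefore the unadmitted case without marked vision loss at presentation, or with the visual result still open. Two investigators could reasonably classify such a case differently.

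**Step 2: follow the case if it is not classed as serious.** Prompt IRB notice is not triggered, and neither is as-they-occur DSMC review. No other section gives an expedited DSMC route for an ocular event. What remains is tabulation and the 6-monthly review.

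**Step 3: size of the wait.**

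- Maximum wait = one review interval = 6 months.
- Mean wait, if events fall evenly between reviews = 6 / 2 = 3 months.
- Maximum wait as a share of the treatment course = 6 / 9 = 0.67, or two-thirds.

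These are waits for cases that stay classed as non-serious. A case later reclassified because vision is lost would enter the fast route at that point.

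**Step 4: how broad can a remedy be?** A general criterion, such as any event needing intervention to prevent permanent vision loss, might also take in pressure elevation, which is the primary endpoint. From Section 3.2, the control rate is 20% and the odds ratio 0.25.

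- Control odds = 0.20 / 0.80 = 0.25.
- Netarsudil odds = 0.25 × 0.25 = 0.0625.
- Netarsudil rate = 0.0625 / 1.0625 = 5.9%.
- With 186 / 2 = 93 eyes per arm, expected endpoint eyes = 93 × 0.20 + 93 × 0.0588 = 18.6 + 5.5 = about 24.

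Not all 24 would meet a general criterion, but its wording would give no clear way to separate them. Graft detachment and rejection could be drawn in too. The remedy has to name events.

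**The case against.** The strongest objection is that the definition is silent on sight but does not exclude it. Calling an event anticipated does not stop an individual case from being serious, and significant disability can cover marked vision loss on the day the patient is seen. That stands. A reader might infer that these events can never be serious at onset; the documents do not support that. They support only that such events need not be.

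The second objection is that other safeguards exist. Table 1 records adverse events at every visit from randomization. Section 4.2 requires the investigator to monitor subjects and to treat eye-related events or refer the rest. Section 4.4 lets the investigator or Sponsor terminate for unacceptable risk without waiting for the DSMC, and nothing forbids earlier voluntary notice. That also stands: the delay is in independent review, not in all safety action.

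Two further inferences are tempting. One is a count of eyes randomized while a signal waits. The protocol states neither an accrual period nor rates for these events, so any such count would rest on assumptions from outside it. The other is that all the serious harm expected from the drug is ocular. The protocol does not say so, and it does not attribute the rare-event list to netarsudil.

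None of this closes the remaining gap. A site can follow the text exactly and still hold an endophthalmitis case until the next scheduled meeting.

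**Conclusion.** The point holds in a limited form. The closed, outcome-based definition allows an acute sight-threatening event, treated without admission and with a good or unknown visual outcome, to bypass both fast routes. The consequence is a DSMC wait of at most 6 months, and about 3 on average under even timing. This rests on reading the list as complete, which is how it is written, and on no voluntary early notice being given.

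It is not a contradiction or a calculation error. It does not affect the primary analysis or the care of the individual patient. It is a cheap improvement to safety oversight.

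**What to change.** Add one criterion to the definition in 4.1: *an acute sight-threatening event in the study eye, namely endophthalmitis, retinal detachment or infectious keratitis*. These events then follow the existing IRB and DSMC as-they-occur routes, and 4.2 needs no change.

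In the same place, state that pressure elevation meeting the primary endpoint, and the ordinary anticipated events in 4.1 (including graft detachment, rejection and graft failure), are not serious on this criterion alone. They would still be serious if they met one of the existing outcomes.

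The cost is about two sentences and a few more expedited reports, of events that the protocol calls rare. No visit, treatment rule or analysis changes.
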